Images from ⁶⁸Ga-PSMA PET/CT scanning will be interpreted by two experienced nuclear medicine physicians (one at the local scanning site as well as central reporting by an expert nominated from the PSMA imaging subgroup). All LNs with increased ⁶⁸Ga-PSMA accumulation will be assigned to their respective anatomical location, measured in the short axis, along with an assigned SUVmax for each affected LN. In addition, visual analysis of the ⁶⁸Ga-PSMA uptake will included a four-point certainty scoring scale (definitely negative, equivocal probably negative, equivocal probably positive, definitely positive). Although not our primary research focus, PSMA +ve lesions within the prostate will be categorised as either focal or diffuse. Disease involving only one of the four prostatic quadrants will be considered as focal. If prostatic lesions are detected in more than one quadrant, the disease will be classified as diffuse/multifocal (if non-contiguous). Signals that indicate potential distant metastatic sites will also be scored using the four-point certainty scoring scale as described above for pelvic nodes [13].

Attention will be paid to ensure comparable imaging protocols are used across participating sites to ensure data obtained are suitable for objective and robust reporting of PSMA PET/CT across the study. Lesion uptake will be categorised according to a predefined anatomical scoring template.

Image scoring

Interpretation of PET imaging will be performed in accordance with the NCRI PET framework. All positive LNs on ⁶⁸Ga-PSMA PET/CT will be assigned to the respective anatomical region: left/right external iliac; left/right internal iliac, left/right obturator; left/right fossa of Marcille. Positive matching will be defined as the correlation between PET scan positivity and histological positivity, with histopathological analysis of the LNs considered the reference standard. Positive nodes in each nodal region/chain will be scored individually. These data can then be analysed separately or collectively for each nodal region. Once recruiting sites have satisfied QC evaluation by the UK PET Core Lab, the SUV values will be generated by identical (or very similar) reconstruction algorithms and are expected to be reproducible across the study.

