8.1. Data Collection

Data generated will be collected by SCTRU, who will be responsible for checking the data, entering it on the trial database and validating it. The data collected will include:

- initial clinical details at enrolment
- outcome of surgical procedure
- outcome of histopathology evaluation of surgical specimens
- PSMA PET/CT report

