9.3. Analysis Plan

A binary logistic regression model will be trained on the SUV values obtained from the PSMA PET/CT imaging to predict whether metastatic disease is present or not. The analysis will be carried out on a (i) per-patient, (ii) bilateral side, (iii) LN-region, and (iv) LN-specific basis (as previously described by Leeuwen et al [9]). Where necessary, a generalized estimating equation model will be used to adjust for correlations within regions of each patient. Performance on unseen data will be assessed using 10-fold cross validation, and calculating sensitivity, specificity, positive predictive value (PPV) and negative predictive value (NPV). The "gold standard" assessments to which the model predictions will be compared will be provided by pathology.

Comparison of PSMA PET/CT reporting between local nuclear physician evaluation and review by central experts will be represented in a Bland Altman plot. A consensus will be developed in terms of minimum training required for local nuclear physicians in the review of PSMA PET signals.

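### Section 9.3 announces a consensus on minimum training for local readers, but its only reader comparison shows how far readers differ, not which of them is right

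*Protocol*

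**What the plan says.** Section 9.3 (Analysis Plan) gives reader agreement two sentences. The first is the comparison: "Comparison of PSMA PET/CT reporting between local nuclear physician evaluation and review by central experts will be represented in a Bland Altman plot". The second is the output: "A consensus will be developed in terms of minimum training required for local nuclear physicians in the review of PSMA PET signals". It does not say how the consensus will be reached.

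Section 3.1 describes the reading. Scans "will be interpreted by two experienced nuclear medicine physicians", of whom one reads locally and the other is a central expert. The level of experience is not defined. Under Image scoring, the same section assigns positive nodes to left and right external iliac, internal iliac, obturator and fossa of Marcille regions. It defines matching of scan to pathology with "histopathological analysis of the LNs considered the reference standard", but does not say whether the local or the central read is matched. Surgical specimens are submitted under the same region labels, and histopathology is planned for all enrolled patients.

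In section 9.3 pathology serves as the gold standard for the predictions of the logistic model. It is not applied to the calls of either reader.

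Section 8.1 lists four data items after the words "The data collected will include": enrolment details, surgical outcome, histopathology outcome and the PSMA PET/CT report. None is reader experience.

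**The concern.** A recommendation on training should rest on where local readers go wrong. A local-central difference does not show that: the local reader may be wrong, the central reader may be wrong, and where both are wrong in the same way there is no difference to see. The last case is not remote. In the surgical series described in section 1.3, the scan was negative in 8 of 12 node-positive patients. Two readers could agree closely on such scans and the plot would look reassuring.

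The training statement bears on primary outcome 2 (best practice for multi-centre PSMA PET/CT) and on the quality assurance named in secondary outcome 1. A minimum put forward next to a plot in the analysis plan could be taken into the future randomised trial as a study finding, when the study has no analysis behind it that concerns training.

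**Working it through.** The protocol gives no figure for reader agreement or for the training minimum, so there is nothing to reproduce. The check compares the planned output with the planned data, followed by two illustrations of size.

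**1. What each element can show.**

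| Element | Where | What it shows |
|---|---|---|
| Local v central, Bland-Altman | 9.3 | Mean difference and spread between readers; neither is the reference |
| Pathology as gold standard | 9.3 | Accuracy of the logistic model, not of a reader |
| Scan-histology matching | 3.1 | Accuracy of a read, but whose read is not stated |
| Reader training against performance | none | – |

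The data for a comparison of each reader with histology are already planned: local and central reads, and histology by region. There are 4 regions on 2 sides, so 8 per patient and 60 × 8 = 480 regions if all 60 patients contribute.

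**2. Could a training threshold be estimated?** The number of local readers is not stated. Suppose k readers and a correlation between training and performance tested at two-sided 5%. The critical value is |r| = t / √(k − 2 + t²), with t the 97.5% point on k − 2 degrees of freedom.

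- k = 4 (one per centre): 4.303 / √(2 + 18.51) = 0.95
- k = 8 (two per centre): 2.447 / √(6 + 5.99) = 0.71
- k = 12 (three per centre): 2.228 / √(10 + 4.96) = 0.58

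So even with experience recorded, only a near-perfect or very strong relation would be detected.

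**3. What the plot can deliver.** Assume one continuous value per patient. The 95% half-width, in SDs of the differences, is t/√n for the bias and t·√(1/n + 1.96²/(2(n − 1))) for each limit of agreement.

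- n = 60: bias 2.001/√60 = 0.26; limits 2.001 × √(0.0167 + 0.0326) = 0.44
- n = 15 (one centre, equal accrual assumed): bias 2.145/√15 = 0.55; limits 2.145 × √(0.0667 + 0.1372) = 0.97

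The plot can describe disagreement over the whole study fairly well and by centre only roughly. At no sample size does it show which reader is right.

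**4. How much the added comparison could show.** The share of positive regions is not given. If 5–20% of 480 are positive, there are 24–96, clustered within patients. Only the discordant ones among these separate the readers on sensitivity, so that comparison will be mainly descriptive.

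**The case against.** **The text promises a consensus, not a calculation.** This stands. A consensus may draw on judgement, core-lab experience, the agreement data and pathology, so it would be too strong to say that it has no data behind it. What is absent is a planned analysis that tells the consensus which local calls were wrong.

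**The data list is not exhaustive, and experienced is undefined.** Both are fair. Local readers may differ in PSMA PET experience, and reader fields may be set out in a CRF or an imaging manual. Their absence from section 8.1 is therefore not an error in itself.

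**Stronger readings that the protocol does not support.**

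- A reader might infer that the central read is taken as truth, because training is directed only at local readers. No section says so. Sections 3.1 and 9.3 name pathology, and a Bland-Altman plot treats neither reader as the reference.
- A reader might see a conflict between "central reporting by an expert nominated from the PSMA imaging subgroup" in section 3.1 and the plural central experts in section 9.3. One expert per scan and several over the study satisfies both.
- A reader might put a number on false training need. Let p be the share of positive regions, and assume sensitivity/specificity of 0.50/0.90 locally and 0.60/0.95 centrally. If the reads are independent given true status, the local reader is right in [p·0.50·0.40 + (1 − p)·0.90·0.05] / [that + p·0.50·0.60 + (1 − p)·0.10·0.95] of discordant regions. This is 0.33, 0.34 and 0.36 for p = 0.05, 0.10 and 0.20, and 0.50 if the readers are equally accurate. But both readers view the same scan. With greater dependence the cells in which only the local reader is right shrink from 0.20 (positive regions) and 0.045 (negative regions) towards 0, and the cells in which only the central reader is right shrink from 0.30 and 0.095 to 0.10 and 0.05. The share in the unequal case can then lie anywhere from 0 to about a third, and the 0.50 holds by symmetry for any two equally accurate readers. It cannot be said that a third to a half of the apparent training need would be false.

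**Conclusion.** The concern holds in a limited form. Section 9.3 links a training output to a comparison that shows disagreement only, while the reference standard that could resolve the disagreement is collected for the same regions and is not applied to the readers. No planned analysis relates training to performance. With about four readers (an assumption) none could reliably estimate a threshold, so any minimum level will be expert opinion and should be labelled so.

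This is a cheap improvement to a descriptive output of a feasibility study. It does not affect the primary question on PSMA expression and nodal disease, and no numerical error is alleged. The conclusion rests on the wording of sections 3.1, 8.1 and 9.3. The illustrations rest on the assumed reader numbers, one continuous value per patient in the plot, equal accrual by centre, and 5–20% of regions positive.

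**What to change.** Keep the Bland-Altman plot and the training deliverable. Add to section 9.3 text to this effect:

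*Local and central calls for each nodal region will each be compared with histology. Sensitivity and specificity will be reported for each read, with a paired comparison that accounts for clustering of regions within patient. A table of discordant regions will show which read histology supported. The consensus on training will draw on local calls that histology contradicts. Any minimum training level is expert consensus and not an estimate from the study data.*

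The generalised estimating equations already named in section 9.3 can handle the clustering. Reporting both reads against histology also helps with interpretation: a deposit missed by both readers may be below what the scan can show (section 1.3 reports that undetected deposits were smaller), whereas one missed only by the local reader points more directly to training.

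The cost is a little more analysis of reads and histology already planned, with no extra patients, scans or readers. The downside is limited information: discordant or positive regions may be few, so the comparison will be largely descriptive.

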9.4. End of Study

This study will end when the following criteria are deemed completed by the sponsor:

- Last patient has attended his last study 'visit' (6 week post-surgery follow up appointment).
- The database has been cleaned and 'locked down' for analysis.

10. ACCESS TO SOURCE DATA/ DOCUMENTS

The investigator, by accepting to participate to this protocol, agrees to co-operate fully with any quality assurance visit undertaken by third parties, including representatives from the Sponsor, SCTRU or the Coordinating Centre or company supplying the product under investigation, as

well as to allow direct access to documentation pertaining to the clinical trial (including CRFs, source documents, hospital patient charts and other study files) to these authorised individuals.

11. QUALITY CONTROL AND QUALITY ASSURANCE

Quality control will be maintained through adherence to the Principles of ICH GCP (Appendix 2) and the SCTRU or coordinating centre's SOPs. The coordinating centre will monitor receipt of CRFs and evaluate incoming CRFs for compliance with the protocol, inconsistencies and missing data.

11.1. Monitoring Visits

The trial will be monitored by SCTRU according to SCTRU SOPs. The frequency and objectives of monitoring will be detailed in the Clinical Monitoring Plan, and may include a Site Initiation Visit, Interim Monitoring Visits and a Close out Visit, which will be performed remotely. As a guideline, the frequency and nature of visits will depend on resource, recruitment and site performance. Higher levels of monitoring will be performed, if requested, by the Data Monitoring Committee, or if the investigators, the Trial Management group or Trial Steering Committee identify particular safety issues.

The objectives of the monitoring plan will be to ensure the safety and wellbeing of trial participants, the accuracy, completeness and consistency of data, adherence to the protocol and compliance with Good Clinical Practice. The monitor will have full access to the Case Report Forms and the participant's medical records (as described in section 10), in accordance with the terms of Informed Consent; as well as all trial related files and documents.

11.2. Data Monitoring Committee

An independent Data Monitoring Committee will be established and will meet after 30 patients have been recruited or in the sixth month of the study, whichever comes first. The Data Monitoring Committee will then meet six monthly. The Data Monitoring Committee membership will include independent members with the CI and Trial Coordinator attending the open sessions only. The committee will receive reports from the SCTRU submit its comments and recommendations to the Trial Steering Committee. The Data Monitoring Committee may choose to see the final results and comment on these prior to publication.

11.3. Trial Steering Committee

A trial steering committee will be established to provide overall supervision of the trial, in particular; trial progress, adherence to protocol, patient safety, and consideration of new information. The committee will meet after the first 30 patients have been recruited then again once recruitment has been completed. Additional meetings will be convened if required. The meetings of the committee will be coordinated to follow on from the DMC meetings.

12. ETHICAL CONSIDERATIONS

Ethical approval by a Research Ethics Committee will be secured before the trial can be started. The trial will be carried out according to guidelines of good clinical practice (GCP) as defined by paragraph 28 and Schedule 1 Part 2 of the Medicines for Human Use (Clinical

Trials) Regulations, 2004, and the Clinical Trials Directive (2001/20/EC) elsewhere in the European Union and follow the principles of research governance.

12.1. Patient Confidentiality

The patient's full name, date of birth, hospital number and NHS number (Community Health Index and/or hospital number in Scotland) will be collected to enable tracing through national records. The personal data recorded on all records will be regarded as confidential, and to preserve each patient's anonymity, only their initials will be recorded on CRFs with the exception of the enrolment CRF which will contain the patients date of birth as this is required to check the inclusion criteria. The patients will be identified within the CRFs by the use of a unique trial number allocated to them upon entry into the study.

The Principal Investigator (or designee) at each site must keep a log of patients' trial numbers, names, addresses and hospital numbers. The Principal Investigator must ensure that patient confidentiality is maintained and that all trial documents (e.g. consent forms) are maintained in strict confidence.

SCTRU will maintain the confidentiality of all patient data and will not reproduce or disclose any information by which patients could be identified. Patients will only be referred to by Trial Number and Initials in any essential trial related correspondence, including Case Report Forms.

All patient identifiable data will be handled, computerised and stored in accordance with the GDPR and Data Protection Legislation and PHS Data Protection Policy.

12.2. Informed Consent

All patients will be informed of the aims of the study. the procedures and possible hazards to which they will be exposed. They will be informed as to the strict confidentiality of their patient data, but that their medical records may be reviewed for trial purposes by authorised individuals other than their treating physician. It will be emphasized that the participation is voluntary and that the patient is allowed to refuse further participation in the protocol whenever they want. This will not prejudice the patient's subsequent care.

Documented informed consent must be obtained for all patients included in the study before they are enrolled. This must be done in accordance with the national and local regulatory requirements and must conform to guidelines on Good Clinical Practice.

All Patient Information Sheets & Informed Consent Forms will be version controlled and dated and this information will always be stated in any communication with ethics committees

13. RESEARCH GOVERNANCE

13.1. Institution and Investigator Selection

Chief Investigator – The Chief Investigator will have overall responsibility for the design, coordination and management of the study. These include:

Trial authorisation including responsibility for the protocol and obtaining approvals

• Ensuring that the trial is conducted according to Good Clinical Practice (GCP)

13.2. Trial Organisation

Sponsor – PHS will act as study sponsor. Central study co-ordination, data collection, monitoring and organisation of the data for the statistical analyses will be undertaken by SCTRU, which has processes in place to ensure that the study will not open to recruitment until appropriate approvals and authorisations have been obtained from the independent research ethics committee, and NHS Research and Development departments.

Clinical Trials Unit – The Sponsor has delegated the responsibility for overall project management, data management and monitoring to Scottish Clinical Trials Research Unit, Public Health Scotland. Responsibilities include:

- a. Assistance with completion of the IRAS form and REC communication
- b. Production of trial specific documentation (i.e. CRFs)
- c. Facilitating set up of trial centres
- d. Data management
- e. Financial Management
- f. Monitoring

Statistical Analysis

The final analysis will be carried out once the last patient has been reviewed at the first postsurgery follow up outpatient appointment, and all data deemed 'cleaned' and the database is locked.

Local Project Teams – These will consist of Urological Surgeons and/or Oncologists (responsible for introducing the patient to the study and ensuring eligibility and consent), Research Nurse (responsible for patient recruitment, obtaining consent and co-ordination of all aspects of data collection), Pathologists (responsible for tissue sample analysis), Radiologists and Radiographers (responsible for completing MRI and CT scans to local standard of care protocol). Investigators at the participating centres are responsible for conducting the trial in accordance with the protocol, Standard Operating Procedures (SOPs), the trial agreement and Good Clinical Practice.

Trial Steering Committee (TSC) – The Trial Steering Committee including members of the research team and an independent Chair, will be responsible for the progress and conduct of the study to provide overall supervision of the trial, in particular; trial progress, adherence to protocol, patient safety, and consideration of new information. The committee will meet after the first 30 patients have been recruited then again once recruitment has been completed. Additional meetings will be convened if required. The meetings of the committee will be coordinated to follow on from the DMC meetings.

Trial Management Group (TMG) – A Trial Management Group (TMG) will meet at month three and thereafter at 6 monthly intervals, with additional meetings if deemed necessary.

Data Monitoring Committee (DMC) – A Data Monitoring Committee will meet after 30 patients have been recruited or in the sixth month of the study, whichever comes first. The Data Monitoring Committee will then meet six monthly to review all data. Once all data have been collected, the DMC will meet every three months (or as necessary) to assess model performance

14. FINANCING AND INSURANCE

This study has been developed through multi-centre cross-disciplinary efforts among the CRUK Cancer Imaging Centres Network in collaboration with the study CI, and is funded by CRUK. Indemnity for participating hospitals is provided by the usual NHS indemnity arrangements.

15. PUBLICATION POLICY

All presentations and publications relating to the trial must be authorised by the Trial Management Group. The main trial results will be published in the name of the trial in a peer-reviewed journal, on behalf of all collaborators. The manuscript will be prepared by the Trial Management Group representatives from SCTRU and high accruing clinicians. The trials offices and all participating Centers and clinicians will be acknowledged in this publication. Any data that might detrimentally affect the progress of the trial will not be released prior to the end of the trial. No investigator may present or attempt to publish data concerning their patients, which is directly relevant to the questions posed in the trial, until the main results have been published.

Appendix 2– The Principles of ICH Good Clinical Practice

- 1. Clinical trials should be conducted in accordance with the ethical principles that have their origin in the Declaration of Helsinki, and that are consistent with GCP and the applicable regulatory requirement(s).
- 2. Before a trial is initiated, foreseeable risks and inconveniences should be weighed against the anticipated benefit for the individual trial subject and society. A trial should be initiated and continued only if the anticipated benefits justify the risks.
- 3. The rights, safety, and well-being of the trial subjects are the most important considerations and should prevail over interests of science and society.
- 4. The available nonclinical and clinical information on an investigational product should be adequate to support the proposed clinical trial.
- 5. Clinical trials should be scientifically sound, and described in a clear, detailed protocol.
- A trial should be conducted in compliance with the protocol that has received prior institutional review board (IRB)/independent ethics committee (IEC) approval/ favourable opinion.
- 7. The medical care given to, and medical decisions made on behalf of, subjects should always be the responsibility of a qualified physician or, when appropriate, of a qualified dentist.
- 8. Each individual involved in conducting a trial should be qualified by education, training, and experience to perform his or her respective task(s).
- 9. Freely given informed consent should be obtained from every subject prior to clinical trial participation.
- 10. All clinical trial information should be recorded, handled, and stored in a way that allows its accurate reporting, interpretation and verification.
 - This principle applies to all records referenced in this guideline, irrespective of the type of media used.
- 11. The confidentiality of records that could identify subjects should be protected, respecting the privacy and confidentiality rules in accordance with the applicable regulatory requirement(s).
- 12. Investigational products should be manufactured, handled, and stored in accordance with applicable good manufacturing practice (GMP). They should be used in accordance with the approved protocol.
- 13. Systems with procedures that assure the quality of every aspect of the trial should be implemented.
 - Aspects of the trial that are essential to ensure human subject protection and reliability of trial results should be the focus of such systems.
